6.6. Primary Efficacy Analysis

The primary objective of the study is to compare the clinical performance of the Philips MicroDose tomosynthesis system (tomosynthesis with a synthetic 2D) images and 2D FFDM system. The primary endpoint is the Area under the ROC curve (AUC) using patient as the unit of analysis. The ROC curves will be generated using the confidence scores (1 to 100) and the reference standard (i.e., normal/benign or cancer). All subjects with both Philips MicroDose tomosynthesis system and FFDM evaluation (modified intent to treat, MITT). For subjects with negative outcome for whom a 1 year follow-up is required, missing values will be removed from the study database.

Smooth ROC curves and area under the curve will be estimated from the CS for each study reader interpreting images acquired with the Philips MicroDose tomosynthesis system and the FFDM

Philips Mammography Solutions Sweden	Clinical Investigation Plan Comparison of the Philips MicroDose Tomosynthesis System to 2D Digital Mammography	DOC-MTIN-9RWH8K- 8.0 Page 29 of 38
---	---	--

systems. If smooth ROC curves cannot be fitted for each reader in each condition (e.g., if there is perfect performance), nonparametric methods may be used. Results will be summarized across readers using the method of [10] which includes random effects for study readers and uses the jackknife to handle correlation within cases, as obtained in the corresponding OR-DBM MRMC software. Robustness of the statistical method may be explored through use of the ANOVA model of Obuchowski and Rockette [11]; this model includes random effects for study readers, and adjusts variances and hypothesis tests for correlations due to having each reader interpret the same case sample. The degrees of freedom may be adjusted as suggested by Hillis [14]. The average AUC for Philips MicroDose tomosynthesis system and the FFDM, the average difference between the two systems, and its standard error for use in computing confidence interval and to performing hypothesis tests for the difference will be estimated.

The following hypothesis will be evaluated:

- Null Hypothesis: $H_0: \Theta_2 - \Theta_1 \geq 0.05$
- Alternative Hypothesis: $\Theta_2 - \Theta_1 < 0.05$

Where Θ_1 is the average AUC for readers using the Philips MicroDose System (tomosynthesis + synthetic 2D) and Θ_2 is the average AUC for readers using the FFDM System. The Philips MicroDose tomosynthesis system will be considered non-inferior to the FFDM if the upper limit one-sided 95% CI for the difference in AUCs is less than 0.05. AUC for Philips MicroDose tomosynthesis system and the FFDM will be also be presented by readers.

6.7. Effect of Missing Values on Primary Efficacy Analysis

To evaluate the effect of possible missing assessment for the reference standard (e.g., subjects does not return for one 1 year follow-up exam) sensitivity analysis will be performed to with missing values assigned as negative outcome, $n - 1$ assumed to be negative and 1 positive in random order, or excluded from analysis.

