5.4.2.3. Matching Reader Indicated Lesion Locations to Truth

For all cancer cases, the lesion location(s) provided by the readers will be assessed for correspondence to the known cancer locations. For purposes of analysis, the cases which the reader assigns a score of BI-RADS 3 or higher and which correspond to the known cancer location (as described below) will be considered as correctly localized.

5.4.2.4. Correct Localization:

A reader will get credit for correct localization of a cancerous lesion if the laterality matches the true laterality of the cancer and any of the three rules below apply:

- Reader recorded lesion at a specific o'clock location anywhere from 1 to 12 is the same as the o'clock location documented by the truther within 2 o'clock ticks.
- Lesions indicated by the truther as being located in the Subareolar region that is reported as Subareolar by the reader.
- Lesions indicated by the truther as in the Axillary Tail region must be reported in either the Axillary Tail or 10, 11, or 12 o'clock (right breast) or 12, 1, 2 (left breast) by the reader.

5.4.3. **Case selection - Image Reading**

Cases for the reader study will be selected from all of the cases acquired through the case acquisition phase. A total of approximately 65 cancers, 40 cases with benign biopsies and 300 normal cases will be selected in sequential order to fulfill the requirements for case stratification. The 300 normal cases will include some cases that were recalled from screening but ultimately determined to be normal after additional work-up, as well as cases that were not recalled from screening. Approximately 10% additional cases will be included to protect from loss to follow-up prior to 1 year status verification.

Case stratification is described in detail in 5.4.6. In summary, cancer cases will be stratified by lesion type and size, and breast density. Benign cases will be stratified by lesion type and breast density. Normal cases will be stratified by breast density and by the recommendation for additional work-up after screening. Once the target case number is reached data collection will stop.

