6. STATISTICAL CONSIDERATIONS

6.1. Sample Size and Number of Readers Justification

6.1.1. Sample Size Justification for Primary Efficacy Analysis

The primary endpoint is the Receiver Operator Characteristics curve analysis for both tests. In this trial, the 2D is the control test, and the tomosynthesis and synthetic 2D is the experiment test. The plan is to enroll approximate 800 patients, to include 65 patients with cancer, 40 biopsy-proven benign cases and 300 normal cases. The evaluations will be based on paired-cases and paired-readers that is all readers will interpret the test results of all patients in both tests (i.e., Philips MicroDose tomosynthesis system and FFDM).

The sample size (number of readers) for the Reader Study is estimated based mixed-effects model for the diagnostic accuracy of a reader j using a particular diagnostic test i on reading occasion q as proposed by Obuchowski [11]. The mixed model is specified as follows:

$$\hat{\theta}_{ijq} = \mu + \mu_i + r_j + (ur)_{ij} + \epsilon_{ijq}$$

Here, $v_i = \mu + \mu_i$ is the mean accuracy of test i (fixed effect), r_j is a random effect for reader j , $(ur)_{ij}$ is an interaction term for readers and tests (random effect), and ϵ_{ijq} is an error term.

An F-statistic with 1 and $(J-1)$ degree of freedom (df) will be used for testing the null hypothesis that the mean diagnostic accuracies of the tests are equal, where J is the number of readers. Under alternative hypothesis, the test statistic follows a non-central F distribution with 1 and $(J-1)$ df, and the non-centrality parameter is estimated as following:

$$\hat{\lambda} = \frac{J(\mu_1 - \mu_2)^2}{2\{\hat{\sigma}_b^2(1 - \hat{\rho}_b) + \frac{\hat{\sigma}_w^2}{Q} + \hat{\sigma}_c^2[(1 - \hat{\rho}_1) + (J - 1)(\hat{\rho}_2 - \hat{\rho}_3)]\}}$$

Philips Mammography Solutions Sweden	Clinical Investigation Plan Comparison of the Philips MicroDose Tomosynthesis System to 2D Digital Mammography	DOC-MTIN-9RWH8K- 8.0 Page 25 of 38
---	---	--

Thus, to calculate the statistical power, multiple parameters in the equation above need to be estimated. For this study, these estimates are based on the following assumptions:

- The type I error: $\alpha = 0.05$
- AUC for control test: $A = 0.85$
- Number of positive patients: $n_1 = 65$
- Number of negative patients: $n_2 = 300$
- Non-inferiority margin: $\Delta = 0.05$
- Variability between readers: $\sigma_b^2 = 0.0009$
- Variability within the reader: $\sigma_w^2 = 0.000225$

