6.2. General Statistical Considerations

The primary analysis will be performed including all subjects selected for the reading portion of the study with confidence score for both Philips MicroDose tomosynthesis system and FFDM evaluation (modified intent to treat, MITT). For this analysis patient will be the basis for the analysis. Non-cancer cases, with missing one year follow-up will be assumed as cancer free case. Missing values will be assumed to be missed at random.

The analysis of safety includes all enrolled subjects in the acquisition portion of the study.

Continuous variables will be summarized using the number of non-missing observations, mean, standard deviation, 95% Confidence Interval (CI) for the mean, median, minimum, and maximum; categorical variables will be summarized using the frequency count and the percentage of subjects in each category. Analyses will be conducted using SAS® software and OR-DBM MRMC software [12].

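### Section 6.7: the only missing-truth scenario that allows a missed cancer picks that woman at random, with no seed, repetition or summary rule, so it cannot show how far one missed cancer could move the AUC result

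*Combined protocol and SAP*

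**What the plan says.** The stated purpose of section 6.7 is "To evaluate the effect of possible missing assessment for the reference standard", for example when a woman does not return for her one-year exam. It lists three treatments: "missing values assigned as negative outcome"; n − 1 "assumed to be negative and 1 positive in random order, or excluded from analysis". It gives no seed, number of draws, method of combining draws or criterion for judging the outcome.

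The primary handling appears twice, and the two statements differ. Section 6.2: "Non-cancer cases, with missing one year follow-up will be assumed as cancer free case". Section 6.6, on negative cases that need one-year follow-up: "missing values will be removed from the study database".

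Loss to follow-up is foreseen in section 5.4.3: "Approximately 10% additional cases will be included to protect from loss to follow-up prior to 1 year status verification".

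The result being checked is a threshold comparison in section 6.6: "The Philips MicroDose tomosynthesis system will be considered non-inferior to the FFDM if the upper limit one-sided 95% CI for the difference in AUCs" is below 0.05.

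**The concern.** Two of the three scenarios repeat handling already in the plan: all-negative is the rule in 6.2 and exclusion is the rule in 6.6. Whichever proves to be primary, one scenario duplicates it and the other is the alternative. Neither lets a woman without follow-up have cancer, so the one-positive scenario carries all the information about a missed cancer.

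If one woman is drawn at random and the analysis is run once, the answer belongs to that woman. Another draw gives another AUC difference and another upper limit. One draw cannot show how large the effect of a single missed cancer could be. An unstated seed also invites questions if it is chosen after the scores are known.

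**Working it through.** **Inputs from the plan.** 18 readers, 65 cancers, 300 normal and 40 benign cases (340 non-cancers), control AUC 0.85, margin 0.05, one-sided 95% upper limit for FFDM minus Philips (sections 6.1.1 and 6.6).

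**Assumed n.** The plan gives no count of women with missing truth. Its 10% allowance would give 30 (of 300) to 34 (of 340). Section 5.4.3 offers this as over-inclusion, not as a forecast, so smaller n is also shown.

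**The plan's own figure.** Section 6.7 states none. The nearest is 18 readers for power of at least 0.80. With the formulas of section 6.1.1 and Q = 1:
- Case variance at 65/300 is 0.00109.
- SE² = (2/18) × [0.0009 × 0.5 + 0.000225 + 0.00109 × 0.54] = 0.000140, so SE ≈ 0.0118.
- Power is about 0.98 (F test at 0.05) or 0.99 (one-sided 0.05). The 0.80 target is met with room to spare.
- The one-sided half-width is about 0.021, so non-inferiority passes when the observed difference is below about 0.029.

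**Chance that one draw misses the most adverse woman.** This is 1 − 1/n and needs no variance assumption (second column of the table).

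**Hard limit for one relabelled woman.** Let d be the difference (FFDM minus Philips) in the share of the remaining 339 negatives that she outscores, and c the difference in the share of cancers that outscore her. Both lie between −1 and 1. Starting from a difference near zero:

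shift ≈ d/66 − (65/66) × c/339

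The first term is at most 1/66 = 0.0152 (30% of the margin). Her removal from the negatives adds at most 65/(66 × 339) = 0.0029. The total is about 0.018 (36% of the margin).

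**Simulated size.** The model had 18 readers, 65 cancers, 340 non-cancers and AUC 0.85 on both modalities, with empirical AUC. Assumed latent variance shares were 0.4 case, 0.2 case-by-modality and 0.4 reader noise. Each of the n women was relabelled in turn. Positive shifts go against Philips.

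| n | Misses most adverse woman | Average worst shift | Average best shift |
|---|---|---|---|
| 2 | 50% | +0.0020 | −0.0018 |
| 5 | 80% | +0.0036 | −0.0040 |
| 10 | 90% | +0.0053 | −0.0049 |
| 30 | 97% | +0.0065 | −0.0068 |
| 34 | 97% | +0.0070 | −0.0070 |

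The SD of a single draw was about 0.003. Between 46% and 52% of draws favoured Philips or changed nothing. At n = 30 to 34, only 15% to 17% of draws reached half of the worst shift, and the best-to-worst spread was 0.013 to 0.014 (26% to 28% of the margin).

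**Sensitivity to the variance split.** A second simulation at n = 34 used shares for case, case-by-modality and case-by-reader of (0.4, 0.05, 0.2), (0.4, 0.15, 0.15) and (0.3, 0.3, 0.1). The single-draw SDs were 0.0017, 0.0028 and 0.0037, and the average worst shifts 0.0041, 0.0063 and 0.0081.

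**When it could matter.** If the SE is unchanged, a shift of 0.007 crosses the threshold only when the observed difference is about 0.022 to 0.036 (0.029 ± 0.007). With a true difference of zero and SE 0.0118, a normal approximation puts that at about 3%. It is higher if Philips is truly somewhat worse.

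**The case against.** Several points against a stronger reading are sound.

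- A reader might infer that the scenario was designed as a worst case and fails at it. The stated purpose is only to evaluate the effect of missing truth; no adverse-case or tipping-point wording appears.
- A reader might take a single draw as the explicit instruction. The wording could also mean permuting or cycling the positive label. Even so, the number of repetitions and the summary remain unstated.
- A reader might infer that any harmful draw has probability 1/n. That figure belongs only to the single most extreme woman; about half of draws go against Philips to some degree. At n = 1 there is no draw, and at n = 2 the miss probability is 50%.
- A reader might infer that the seed decides whether the trial is declared robust. Section 6.7 contains no such verdict, the non-inferiority decision rests on the primary analysis, and the other two scenarios involve no draw.
- The true n may be small. Sections 5.4.6.1 and 5.4.6.2 write one-year confirmation into the definitions of normal-no-recall and biopsy-benign cases.
- The simulations moved the empirical AUC point estimate, whereas section 6.6 plans smooth fitted curves and judges the upper limit.

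These points narrow the concern and weaken its size. They do not supply the missing rule for choosing, repeating and summarising the positive label.

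**Conclusion.** The point holds as a cheap improvement. As written, the one scenario that admits a missed cancer is under-specified. Read as a single draw, it cannot show how much one missed cancer could change the primary result.

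The size is modest: typically about 0.003, on average 0.007 at worst, and never more than about 0.015 to 0.018, against a margin of 0.05. It matters only for a result close to the margin. The 1 − 1/n probabilities depend only on n, and the hard limit only on the case counts and a starting difference near zero. The simulated shifts also depend on assumed variance splits, empirical AUC and an assumed n of up to 34.

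A reader might also infer that one positive is too few. The documents give no cancer rate among women lost to follow-up, so they do not support that. At assumed rates of 0.1% to 2%, 30 to 34 such women would contain 0.03 to 0.68 expected cancers, with a 0.04% to 15% chance of two or more.

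**What to change.** In section 6.7, replace the random choice with an exhaustive rule: label each woman with missing one-year truth as the single positive in turn, with the others negative, and rerun the primary AUC analysis each time. Report the range of the AUC difference and the largest one-sided 95% upper limit beside the 0.05 margin. Present this as a descriptive sensitivity result; the plan does not need a new pass/fail criterion here. A seeded multiple-draw summary would also remove dependence on one draw, but it would not guarantee that the extreme allocation is seen.

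Reconcile section 6.2 (missing assumed cancer free) with section 6.6 (missing removed), so that it is clear which scenarios in 6.7 differ from the primary analysis.

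The cost is a sentence or two of text and some tens of reruns of a programmed analysis at the assumed n, with no new data. The reported worst case may look slightly less favourable than a single random draw.

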6.8. Secondary Efficacy Analysis

The secondary objectives are:

- To compare the average glandular dose for exams acquired on Philips MicroDose Tomosynthesis system and the 2D mammography system.
- To compare the non-cancer recall rate for Philips MicroDose Tomosynthesis system and 2D mammography exams.
- To compare the sensitivity and specificity of the Philips MicroDose tomosynthesis system (i.e., Tomosynthesis and synthetic 2D) to that obtained with 2D mammography.

Secondary objectives will only be tested if the null hypothesis for the primary endpoint is rejected. Four secondary endpoints will be evaluated. To control the Type I error, the following pre-specified order using a gatekeeper procedure as described by Dmitrienko et al. (2007) will be used:

Family	Endpoint	Procedure
F1	AUC ROC	Test at the 0.05 level, no adjustment to the p-value
F2	Radiation Dose	Test only if Ho for AUC ROC is rejected, p-value adjusted using HOLM procedure
	Recall Rate	Test only if Ho for AUC ROC is rejected, p-value adjusted using HOLM procedure
F2	Sensitivity	Test only if any Ho for F2 is rejected, p-value adjusted using HOLM procedure
	Specificity	Test only if any Ho F2 is rejected, p-value adjusted using HOLM procedure

The average glandular dose (i.e., radiation dose) refers to the total radiation dose during the exam and is expressed in mGy. The goal is to compare total radiation dose between the Philips MicroDose tomosynthesis system and the FFDM systems. The following hypothesis will be tested:

The average glandular dose (AGD) will be recorded per subject for each breast (right and left) and view (CC and MLO). The following hypothesis will be evaluated:

- Null Hypothesis: $H_0: \mu_2 - \mu_1 > \delta$
- Alternative Hypothesis: $\mu_2 - \mu_1 \leq \delta$

where μ_1 and μ_2 are the mean average glandular dose (i.e., radiation dose) for the Philips MicroDose Tomosynthesis system and FFDM system, respectively, and δ is 10% of the FFDM radiation dose.

Analysis will be performed using an appropriate analysis of variance. If the required assumptions for the ANOVA are violated, transformation of the data or non-parametric procedures may be used. The 95% confidence interval for the mean difference in radiation dose between the two systems will be constructed. Under this proposal Philips tomosynthesis will be declared as emitting less radiation than the FFDM if the upper bound of the 95% confidence interval for the difference in radiation dose is less than 10% of the FFDM.

The non-cancer recall rate will be recorded per subject. All negative screening, recalled and benign biopsy cases will be included. The following hypothesis will be evaluated:

- Null Hypothesis: $H_0: \pi_2 - \pi_1 = 0$
- Alternative Hypothesis: $\pi_2 - \pi_1 \neq 0$

where π_1 and π_2 are the non-cancer recall rate for the Philips MicroDose Tomosynthesis system and FFDM system, respectively.

Recall rate will be analyzed using the concept of clustered binary data as described by Zhou et al (2011). In this case, each Reader will be considered as multiple observations within the same subject (cluster). The 95% confidence interval for the difference in recall rate will be constructed. If the upper limit to the one-sided 95% Confidence Interval for the difference (Philips minus FFDM) in recall rates among non-cancers is less than 0.05 (delta of 5%), Philips tomosynthesis will be considered as resulting in a similar recall rate to that of 2D FFDM. In addition, a bootstrapping method with replacement will be used to compare average recall rates among all Readers.

The sensitivity or specificity within a reader between the two systems will be estimated, and tested for statistical significance using binomial test for paired data. Results will be summarized across readers using the ANOVA model of Obuchowski and Rockette [11], which applies to any metric of diagnostic accuracy under general conditions. The following hypothesis will be evaluated:

- Null Hypothesis: $H_0: S_2 - S_1 \geq 0.10$

Philips Mammography Solutions Sweden	Clinical Investigation Plan Comparison of the Philips MicroDose Tomosynthesis System to 2D Digital Mammography	DOC-MTIN-9RWH8K- 8.0 Page 31 of 38
---	---	--

- Alternative Hypothesis: $S_2 - S_1 < 0.10$

Where S_1 is average sensitivity/specificity for readers using the Philips MicroDose tomosynthesis system and S_2 is the average sensitivity/specificity for readers using the FFDM. The Philips MicroDose tomosynthesis system will be considered non-inferior to the FFDM if the upper limit one-sided 95% CI for the difference in sensitivity/specificity is less than 0.10.

To evaluate the effect of breast density on ROC AUC for images obtained using Philips MicroDose tomosynthesis system and FFDM, breast density will be stratified as fatty (i.e., BI-RADS breast density type A and B) and dense (BI-RADS breast density type C and D). Analysis will be similar to the described for the primary efficacy analysis.

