5.4.2.2. Suspicious Findings (Recall) Reporting

For each of the image sets, the reader will examine the images and look for any area of concern. For each suspicious lesion(s) triggering the need to recall a patient, the reader will localize the lesion(s) by providing the laterality and an o'clock location, assign a forced BI-RADS® rating, and the confidence score of the lesion being malignant (CS) (51 to 100) will be reported. The score 51 represents the least suspicious recall case, whereas the score 100 represents the most suspicious recall case. The reader will also provide the lesion type and size. After marking and rating all lesions, the reader will be asked to assign an overall BI-RADS® rating and CS score for the whole case. The allowed forced BI-RADS® ratings for suspicious lesion(s) are 3, 4, or 5. BI-RADS® 0 rating is not allowed in this study.

The annotations of suspicious lesion(s) will be made on the softcopy review workstation using the software features of case review application.

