6.1.4. Sample Size Justification for Sensitivity Non-inferiority Analysis

For the sensitivity analysis, the sample size estimation is based on the following assumptions:

- The type I error: $\alpha = 0.05$
- Sensitivity for control test: $Se = 0.85$
- Number of positive patients: $n_1 = 65$
- Non-inferiority margin: $\Delta = 0.10$
- Variability between readers: $\sigma_b^2 = 0.009$
- Variability within the reader: $\sigma_w^2 = 0.00225$
- Correlations: $\rho_1 = 0.46$, $\rho_2 - \rho_3 = 0$
- Correlation: $\rho_b = 0.8$
- Power for the non-inferiority test: $1 - \beta \geq 0.8$

The variance between different patients σ_c^2 will be calculated based on a binomial approximation as follows:

$$\sigma_c^2 = \frac{S_e(1 - S_e)}{n_1}$$

Where S_e is the expected sensitivity and n_1 is the number of positive patients (i.e., patients with cancer).

Philips Mammography Solutions Sweden	Clinical Investigation Plan Comparison of the Philips MicroDose Tomosynthesis System to 2D Digital Mammography	DOC-MTIN-9RWH8K- 8.0 Page 27 of 38
---	---	--

In a previous study on the Philips MicroDose L30 system, the estimated sensitivity was 0.936, with a 95% C.I. (0.897, 0.976) (see Statistics Collaborative, Inc., 2011). In another similar study for the Hologic Tomosynthesis Mammography System, the sensitivity for a 2D system was 0.862 Hologic, Inc. 2012). Based on these previous results, it is expected that the sensitivity for both tests will be approximately 0.85.

In a previous study on Philips MicroDose L30 [19] the estimated σ_b^2 with 95% C.I. was 0.0035 (0.0019, 0.0084). In another similar study for the Hologic Tomosynthesis Mammography System [20] the estimated σ_b^2 with 95% C.I. was 0.0046 (0.0024, 0.0114). Thus a value of 0.009 is a reasonable estimation for σ_b^2 in the proposed study.

The variance within each reader interpreting the results of the same patients σ_w^2 it is assumed to be one-fourth of σ_b^2 , thus 0.0025.

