Correlation for the same patients evaluated by the same reader using different tests (ρ_1), for the same patients evaluated by different readers with the same tests (ρ_2) and for the same patients evaluated by different readers and different tests (ρ_3) are based on suggestions from Obuchowski (2000). The correlation for the same reader to evaluate patients using different tests ρ_b ranges from 0.44 to 0.86 in AUC analysis, according to Rockette et al. (1999 such correlation are usually higher for sensitivity analysis. Thus, it is expected that the value ρ_b will be approximately 0.80 for this study.

Based on these assumptions, for the sensitivity analysis, 18 readers will be required to achieve statistical power of at least 0.80, after adjusting for multiple endpoints.

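### The Section 6.8 gatekeeping scheme does not control Type I error across the secondary endpoints (about 9.75% in a near-worst case), and its fixed 95% bounds conflict with the Holm step

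*Combined protocol and SAP*

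**What the plan says.** Section 6.8 gives the purpose of its testing order: "To control the Type I error, the following pre-specified order using a gatekeeper procedure", with a citation to a multiple-testing text. The table then sets out three blocks:

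- AUC is tested at 0.05 without adjustment.
- Dose and recall rate (F2) are tested with Holm if the AUC null is rejected.
- Sensitivity and specificity, also labelled F2, follow the rule "Test only if any Ho for F2 is rejected, p-value adjusted using HOLM procedure".

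No truncation fraction, carried alpha or confidence level for a Holm step is given.

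The success rules come later in Section 6.8:

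- Dose succeeds if the "upper bound of the 95% confidence interval for the difference in radiation dose is less than 10% of the FFDM".
- Recall has a two-sided null of equal rates. It is then judged by whether the "upper limit to the one-sided 95% Confidence Interval for the difference (Philips minus FFDM) in recall rates" is below 0.05.
- For sensitivity and specificity, the device "will be considered non-inferior to the FFDM if the upper limit one-sided 95% CI for the difference in sensitivity/specificity is less than 0.10".

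Section 6.1.4 says that "18 readers will be required to achieve statistical power of at least 0.80, after adjusting for multiple endpoints", and Section 6.1.5 says the same for specificity.

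**The concern.** There are three linked problems.

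1. **Alpha is used twice.** After one Holm rejection in the dose/recall pair, the other member is tested at the full 0.05. If the next pair opens after any rejection and also receives 0.05, two separate 0.05 chances of a false claim can coexist. An any-rejection rule needs a first-stage procedure that holds back some alpha for the nulls not rejected. Ordinary Holm does not.
2. **Two decision rules.** Holm's first step for a pair works at 0.025. A fixed one-sided 95% bound works at 0.05. Nothing in the plan links the two.
3. **Two recall hypotheses.** Equality and a 5-point margin give different p-values, and the plan does not say which enters Holm. That choice can decide whether sensitivity and specificity are tested at all.

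The stated Type I error control is therefore not delivered in every configuration, and two analysts could draw opposite conclusions from the same data.

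**Working it through.** **1. The plan's own figures.** With 18 readers, one reading occasion and the Section 6.1 formula:

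- Sensitivity: λ = 18 × 0.10² / (2 × [0.009 × 0.2 + 0.00225 + (0.85 × 0.15/65) × 0.54]) = 17.62.
- Specificity: λ = 18 × 0.10² / (2 × [0.012 × 0.2 + 0.003 + (0.70 × 0.30/300) × 0.54]) = 15.58.

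From the noncentral t with 17 df, power at one-sided 0.025 (Holm's first step) is 0.977 and 0.960. The claim of at least 0.80 after adjustment is met. Holm within one pair also works: with both nulls true and independent, the error is 1 − 0.975² = 0.049.

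**2. The full scheme.** Take AUC passed, the dose null false, the recall null true, the sensitivity null true and the specificity null false, with the false nulls rejected almost surely. Dose is rejected, so recall is tested at 0.05 and the next pair opens. Specificity is rejected, so sensitivity is tested at 0.05. Under independence the familywise error is 1 − 0.95 × 0.95 = 0.0975. Under any dependence it is at most 0.05 + 0.05 = 0.10.

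Simulation with 1,000,000 draws, covering all 15 non-empty sets of true nulls:

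| True nulls | Familywise error |
|---|---|
| One of dose/recall plus one or both of sensitivity/specificity | 0.097–0.098 |
| Dose and recall, with or without the others | 0.050 |
| Sensitivity and specificity | 0.049 |
| Any single null | about 0.050 |

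With correlation between the two null tests, 0.0975 falls to 0.095 (ρ = 0.2), 0.088 (0.5) and 0.063 (0.95).

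**3. Can this happen after AUC has passed?** By the plan's formula the AUC λ is 17.81, so the standard error is 0.05/√17.81 = 0.0118, and power at equal AUC is 0.992. Assume a binormal curve with slope 0.6 to 1.2 through the planned sensitivity of 0.85 and specificity of 0.70.

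- Sensitivity 10 points worse with specificity unchanged lowers AUC by 0.059–0.075. Both 10 points worse lowers it by 0.116–0.122. The AUC test then nearly always stops the sequence.
- A shift of cut-point along an unchanged curve is different. Sensitivity 0.75 goes with specificity 0.80–0.87. Specificity 0.60 goes with sensitivity Φ(1.036 + 0.271 × slope), which is 0.885–0.913. AUC passes with probability 0.992, and the error is 0.992 × 0.0975 = 0.097.

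The endpoint definitions allow this. Recall is cut at category 3, since the "ratings for suspicious lesion(s) are 3, 4, or 5" (Section 5.4.2.2), while Section 4.2 cuts sensitivity and specificity at category 4. A change in how readers use 3 versus 4 can move sensitivity and specificity while recall and AUC stay put. Equal recall is a true null only under the two-sided rule. Under the margin rule, recall on the investigational system must truly be 5 points higher.

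**4. Holm against the fixed bounds.** Suppose the one-sided p-values are 0.03 for sensitivity and 0.20 for specificity. Holm gives 2 × 0.03 = 0.06, so neither is rejected. But 0.03 < 0.05 puts the one-sided 95% bound for sensitivity below 0.10, which the plan calls non-inferior.

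If the plain bounds decide, dose and recall both null gives 1 − 0.975 × 0.95 = 0.074 (dose bound from a two-sided interval) to 1 − 0.95² = 0.098 (one-sided), against 0.050 with Holm. The maximum is 1 − 0.95³ = 0.143, with one dose/recall null and both sensitivity and specificity nulls true. The AUC test would rarely let that state through.

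**The case against.** - **The cited text may supply the missing alpha rule.** It cannot be consulted here. The table says only Holm and gives no parameter, so a truncated version cannot be executed from the plan. This point limits the finding to the scheme as written.
- **Both blocks are labelled F2, so one four-way Holm may be meant.** That would control error at 0.05, but making part of a family testable only after a rejection in the same family would be circular. Two families is the natural reading.
- **9.75% is a knife-edge.** This largely stands. It needs a deficit exactly at the margin. With the sensitivity standard error of 0.10/√17.62 = 0.0238, a true deficit of 11, 12 or 13 points gives 0.069, 0.057 or 0.052. It is not the planned state either: Section 6.1.4 says "it is expected that the sensitivity for both tests will be approximately 0.85", and Section 6.1.3 plans on a recall reduction. Recall and specificity share cases and readers, so independence is doubtful for that pair. Even so, strong control means control in every configuration.
- **The bounds may be meant to apply within Holm.** A 95% one-sided bound is right at Holm's second step, so the conflict arises only when the partner endpoint fails. It is still a conflict, and the text does not resolve it. For dose the objection is strong: Section 6.1.2 uses one-sided 0.025, which matches the upper limit of a two-sided 95% interval and Holm's first step. That favours the 0.074 end of the range.

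**Conclusion.** The concern holds. As written, the scheme controls familywise error when all four secondary nulls are true, but not in every configuration. The error is about 0.0975 (ceiling 0.10) when exactly one dose/recall null and at least one sensitivity/specificity null are true. That figure is conditional on AUC having passed, and it assumes independence and near-certain rejection of the false nulls. Correlation, or a deficit beyond the margin, reduces it. After a passed AUC test the realistic route is a shift in the use of category 3 versus 4.

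The conflict between Holm and the fixed one-sided 95% bounds is definite for recall, sensitivity and specificity and needs no unusual scenario. For dose it depends on the unstated sidedness. The doubt over which recall hypothesis is in the family also stands. The primary AUC conclusion is untouched.

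**What to change.** Amend Section 6.8 before the reads are analysed:

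1. Label the sensitivity/specificity pair F3.
2. Keep the any-rejection rule, but use one of these in F2:
   - Truncated Holm with fraction 0.5: steps at 0.025 and (0.5 + 0.25) × 0.05 = 0.0375. Pass 0.5 × 0.05/2 = 0.0125 to F3 after one rejection and 0.05 after both. The case above becomes 0.0375 + 0.9625 × 0.0125 = 0.0495.
   - Bonferroni: 0.025 each. Pass 0.025 after one rejection and 0.05 after both. The case becomes 0.025 + 0.975 × 0.025 = 0.049.

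   In simulation the maximum over all configurations is 0.050 for both.
3. Set each confidence bound at the level reached in the procedure.
4. State which recall hypothesis belongs to F2.

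Opening F3 only after both F2 rejections would also control error. But if the two-sided recall null is kept and recall is truly equal, F3 would open only about 5% of the time. That drawback does not apply under the margin rule.

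No readers or cases are added for sensitivity and specificity. Power at the first Holm step in F3, from the plan's formula with 18 readers:

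| F2 outcome | One-sided level | Sensitivity | Specificity |
|---|---|---|---|
| One rejection, truncated Holm | 0.00625 | 0.904 | 0.860 |
| One rejection, Bonferroni | 0.0125 | 0.949 | 0.920 |
| Both rejections | 0.025 | 0.977 | 0.960 |

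Under truncated Holm, recall's second step falls from 0.05 to 0.0375. Section 6.1.3 does not give the level behind its 80%. If it is two-sided 0.05, power at that step goes from 0.80 to 0.76. If it is 0.025, which fits that section's mention of multiplicity adjustment better, power goes from 0.87 to 0.84.
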